7.8 Procedure(s) to account for missing or spurious data

Any missing data will be imputed in a last observation carried forward model.

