1.7 Table of endpoints/outcomes

Objectives	Outcome Measures	Timepoint of evaluation of this outcome measure
Primary Objective To assess the feasibility of the present trial in terms of participant retention	Participant retention \geq 70%	End of tDCS sessions (visit 21)
Secondary Objective To assess the acceptability of the intervention	Positive endorsement of tDCS sessions as measured by an acceptability questionnaire	End of tDCS sessions (visit 21)

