4.3 The randomisation scheme: N/A

4.3.1 Method of implementing the randomisation/allocation sequence: N/A

4.4 Blinding: N/A

4.5 Emergency Unblinding: N/A

4.6 Baseline data

The baseline data consist of: HRSD, PHQ-9, HAMA, YMRS, SDS, tDCS AEQ, Acceptability questionnaire, EEG (optional) (Appendix 2).

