4.9 Qualitative assessments

At the final tDCS session, participants will complete the acceptability questionnaire and provide feedback on their experience of the study.

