4.10 Withdrawal criteria

Participants will be withdrawn from the trial if they do not comply with the intervention, namely if they are unable to have a minimum of 50% of the tDCS session (10 out of 21 sessions), or if they develop serious adverse effects from any part of the study. Recording of the reasons for withdrawal will be made. Their GP will be informed about their withdrawal, and there will have a telephone follow up at 1 month following their withdrawal.

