7.3.3 Secondary outcome analysis

The secondary outcome analyses will be the percentage of participants rating the intervention as acceptable at the end of the 6 week course of tDCS. The acceptability scale consists of the question 'How acceptable did you find the tDCS sessions?' with responses ranging from 'Very unacceptable' to 'Very acceptable' on a 7-point anchored Likert scale with the acceptable ratings being from rating 5-7.

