7.4 Subgroup analyses: N/A

7.5 Adjusted analysis: N/A

7.6 Interim analysis and criteria for the premature termination of the trial: N/A

7.7 Participant population

All participants will be included in the analysis in an intention to treat analysis and participants who have completed the study will be included in a completer analysis.

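### Blanket LOCF does not exempt the acceptability endpoint, so a baseline or other early rating can be counted as the end-of-course rating

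*Combined protocol and SAP*

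**What the plan says.** All references are to the combined protocol and SAP.

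- **Missing data (7.8).** The whole rule is one sentence: "Any missing data will be imputed in a last observation carried forward model". It names no endpoint and makes no exception.
- **Populations (7.7).** "All participants will be included in the analysis in an intention to treat analysis"; a completer analysis is planned as well. Neither population is assigned to a particular endpoint.
- **Secondary endpoint (7.3.3).** It is "the percentage of participants rating the intervention as acceptable at the end of the 6 week course of tDCS". The item is "How acceptable did you find the tDCS sessions", scored on seven points, with 5 to 7 counted as acceptable. Section 1.7 places the endpoint at visit 21 and describes it as "Positive endorsement of tDCS sessions as measured by an acceptability questionnaire". No target percentage is set.
- **When the questionnaire is given.** Section 4.6 reads "The baseline data consist of: HRSD, PHQ-9, HAMA, YMRS, SDS, tDCS AEQ, Acceptability questionnaire, EEG (optional) (Appendix 2", and section 4.9 adds "At the final tDCS session, participants will complete the acceptability questionnaire". The supplied text dates no other completion. The schedule itself is in Appendix 2, which is not in the supplied text.

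**The concern.** Read together, these sections let the analyst fill a missing visit-21 rating with whatever acceptability rating came last. For an early leaver that may be the baseline one. The endpoint is a judgement on the sessions at the end of the course, and a baseline or other early rating is not that. If it was given before the first session, it cannot answer the question at all, because there was nothing yet to judge. This is more specific than the usual objection to LOCF: a carried baseline depression score at least measures the same construct, whereas a carried acceptability rating may not.

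The other possibility is that the endpoint item is first asked at the final session. LOCF then has nothing to carry, and sections 7.3.3, 7.7 and 7.8 do not say whether the person is left out, counted as not acceptable, or handled in some other way.

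Acceptability is the secondary objective and part of the trial's stated aim, and section 5.3 says the findings will inform the design of a sham-controlled trial. The people affected are mainly those who stopped. Under section 4.10 they include anyone withdrawn because of non-compliance "or if they develop serious adverse effects from any part of the study", and a rating carried for such a person could pre-date the event.

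**Working it through.** **Inputs from the plan.** Enrolment is 30, attrition 20%, and completers 24 (7.1). The retention hypothesis is 70% or more (1.4). Ratings of 5 to 7 count as acceptable (7.3.3).

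**The plan's own figure.** 24 / (1 - 0.20) = 30, which agrees with 7.1. Planned drop-outs: 30 - 24 = 6. At exactly 70% retention: 30 x 0.30 = 9 drop-outs and 21 completers.

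**Weight of one carried rating.** 1/30 = 3.3 percentage points of the all-enrolled percentage.

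**Comparison with the completer analysis in 7.7.** Let n be the completers, d = 30 - n the drop-outs, e the completers rating 5 to 7, p = e/n, and k the drop-outs whose carried rating is 5 to 7 (k from 0 to d).

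- All-enrolled percentage under LOCF: (e + k)/30.
- Completer percentage: p.
- Gap: (e + k)/30 - p. Since e = (30 - d)p, this equals (k - d x p)/30.

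This assumes that every completer has a visit-21 rating, that no drop-out has one, and that all 30 stay in the denominator. The plan gives no value for p, so e is assumed over a range.

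| n | d | e (assumed) | Completer % | LOCF %, k = 0 to d | Gap, points |
|---|---|---|---|---|---|
| 24 | 6 | 12 | 50.0 | 40.0 to 60.0 | -10.0 to +10.0 |
| 24 | 6 | 18 | 75.0 | 60.0 to 80.0 | -15.0 to +5.0 |
| 24 | 6 | 22 | 91.7 | 73.3 to 93.3 | -18.3 to +1.7 |
| 21 | 9 | 11 | 52.4 | 36.7 to 66.7 | -15.7 to +14.3 |
| 21 | 9 | 16 | 76.2 | 53.3 to 83.3 | -22.9 to +7.1 |
| 21 | 9 | 19 | 90.5 | 63.3 to 93.3 | -27.1 to +2.9 |

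Worked example for the second row: p = 18/24 = 0.75 and d x p = 4.5. With k = 0 the gap is -4.5/30 = -15.0 points; with k = 6 it is 1.5/30 = +5.0 points. LOCF exceeds the completer figure only if k is 5 or 6.

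**A completer without a visit-21 rating.** Section 7.8 as written also imputes this person. The carried rating would count for 1/24 = 4.2 points of the completer percentage with 24 completers, so the completer analysis is not wholly free of the problem.

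**The case against.** The strongest reply is that the supplied text does not show an unsuitable rating being available to carry. Section 4.6 says only that the questionnaire is part of the baseline data. The item is worded in the past tense, section 1.6 speaks of acceptability scales in the plural, and section 4.6 also lists the tDCS adverse events questionnaire, so it may simply be naming the instruments. Timing is open too. There are 21 sessions (5.6), the sessions end at visit 21 (1.7), and optional EEG is listed for visit 1 (4.1.3). This suggests that visit 1 may include the first session and that the baseline form could follow it. A reader might infer that drop-outs' pre-treatment expectations will be counted as acceptability; without Appendix 2 the documents do not establish that. What stands is that a rating after session 1 would still not be an end-of-course rating, and that if no earlier rating exists the handling is undefined.

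Second, a completer analysis is already planned, so a largely unimputed figure will sit beside the imputed one. That is fair and limits the harm, although 7.7 does not name it as the analysis for this endpoint and it leaves out those who stopped.

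Third, section 4.2 permits use of data collected before withdrawal only with consent. That may reduce the number of carried ratings, but it does not say how the affected people are counted.

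Fourth, the effect is modest beside sampling error: the exact 95% interval for an assumed 18/24 is 53% to 90%. That also stands.

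**Conclusion.** The point holds as a minor one. Applied literally, the missing-data rule can enter a baseline or other early rating as the visit-21 rating, for drop-outs and completers alike. If there is no such rating, the plan leaves the person's handling open. With completer endorsement assumed at about 75%, the all-enrolled figure differs from the completer figure by -15.0 to +5.0 points with 6 drop-outs and by -22.9 to +7.1 with 9. The endorsement rates and the number of drop-outs carrying 5 to 7 are assumptions.

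Three stronger readings are not supported.

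- A reader might infer that LOCF inflates acceptability by 20 points (6/30) or 30 points (9/30). Those are upper bounds against counting every drop-out as not acceptable, an analysis the plan does not contain. Against the planned completer analysis the overstatement is at most 5.0 or 7.1 points at about 75% endorsement, and LOCF may equally give the lower figure.
- A reader might infer that the plan is silent on a completer with a missing rating. It is not: the wording of 7.8 covers that person.
- A reader might infer that a feasibility decision could be reversed. No acceptability threshold is set, and the primary retention endpoint is not affected.

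**What to change.** In 7.8 and 7.3.3, exempt acceptability from LOCF and state that a baseline rating is never used as the end-of-course value. Then report two figures:

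1. The percentage rating 5 to 7 among participants with an observed end-of-course rating, with the number missing.
2. Beside it, the percentage of all enrolled participants with missing ratings counted as not acceptable, labelled as a conservative sensitivity bound only. It should not be the main figure, because it mixes in retention, which is already the primary endpoint (7.3.2).

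In the assumed examples, with every completer rated and no drop-out rated, the pair would read 75.0% and 18/30 = 60.0% with 6 drop-outs, or 76.2% and 16/30 = 53.3% with 9.

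The cost is a change of wording in two sections, with no added data collection and no change to the sample size. The downside is one extra reported percentage, equal to or lower than the observed one.

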1.6 Exploratory endpoints/outcomes

Exploratory measures:

- i. Trained rater measure of depressive symptoms: Hamilton Rating Scale for Depression (HRSD): The hypothesis is that course of tDCS treatment will improve clinical response as measured by a HRSD score reduction of $\geq 50\%$ following the course of tDCS treatment.
- ii. Self-report measure of depressive symptoms: Patient Health Questionnaire (PHQ-9)
- iii. Trained rater measure of anxiety symptoms: Hamilton Anxiety Scale (HAMA)
- iv. Trained rater measure of manic symptoms: Young Mania Rating Scale (YMRS)
- v. Self-report measure of disability and impairment: Sheehan Disability Scale (SDS)
- vi. tDCS Adverse Events Questionnaire (AEQ)
- vii. Participant acceptability questionnaire scales
- viii. Optional EEG recordings during an eyes-closed resting state for 10 minutes followed by a decision making task (eg. Cheng and Lee, 2015) and an emotional valence categorisation task (eg. Maeoka et al., 2012).

Exploratory outcomes:

- 1) HRSD reduction $\geq 50\%$ following the course of tDCS
- 2) HRSD score ≤ 7 following the course of tDCS
- 3) Improvement in self-reported depressive symptoms as measured by PHQ-9
- 4) Improvement in anxiety symptoms as measured by HAMA
- 5) No significant increase in manic symptoms as measured by YMRS
- 6) Improvement in disability experience as measured by SDS
- 7) Recording of adverse events as measured by the tDCS AEQ
- 8) Measure of neural connectivity using resting state EEG, which has been proposed as potential surrogate outcome measure for clinical applications (Alhaj et al., 2011; Miniussi et al., 2012; Woods et al., 2016). Quantitative EEG analysis of the decision making task (eg. Cheng and Lee, 2015) and emotional valence categorisation task (eg. Maeoka et al., 2012).

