4.8 Long term follow-up assessments

Long term follow-up assessments will be acquired at 3 months and at 6 months following the final treatment visit (Appendix 2).

Participants who do not respond to repeated attempts at contact will be identified as 'lost to follow-up'.

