7 STATISTICAL ANALYSIS PLAN

7.1 Sample size calculation

We will enrol 30 participants with major depression based on a 20% attrition rate to achieve a sample size of 24 participants who will complete the course of treatment, given the exploratory nature of the pilot study.

[figure not shown]

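### Carrying the last value forward for all missing data would put end-of-treatment scores into the 3- and 6-month results for participants lost after the course

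*Combined protocol and SAP*

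**What the plan says.** - **Missing data (7.8).** The whole rule is one sentence: "Any missing data will be imputed in a last observation carried forward model". It makes no distinction by outcome, visit or reason for missingness, and no sensitivity analysis accompanies it.
- **Follow-up (4.8).** Assessments are planned at 3 and 6 months after the final treatment visit, with details left to Appendix 2. Loss is foreseen: "Participants who do not respond to repeated attempts at contact will be identified as 'lost to follow-up". No rate is given for this phase.
- **Symptom outcomes (1.6).** Response is an HRSD fall of at least half. Remission is defined as "HRSD score ≤ 7 following the course of tDCS". Neither names a visit. The table in 1.7 fixes visit 21 for retention and acceptability and has no row for the exploratory outcomes.
- **Analysis sets (7.7).** An intention-to-treat analysis of everyone is planned, plus an analysis of those who completed the study. Completion is not tied to visit 21 or to month 6.
- **Use of the results (5.3).** The study is not sized for efficacy, but its findings are to shape a later multi-site sham-controlled trial.

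**The concern.** Taken literally, 7.8 lets a score recorded at the end of active stimulation stand in for a score up to 6 months later. For anyone lost after improving, a return of symptoms cannot be recorded. For anyone lost without improving, a later recovery cannot be recorded either. The 3- and 6-month summaries would then mix measured outcomes with copies of the visit 21 outcome, and a reader could not tell the two apart.

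What is at stake is what the pilot tells the designers of the next trial about symptoms after treatment stops. The feasibility conclusion is not at stake.

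**Working it through.** **Inputs from the documents.** Enrolment is 30, "based on a 20% attrition rate to achieve a sample size of 24 participants who will complete the course of treatment" (7.1). Follow-up is at 3 and 6 months (4.8). The imputation rule is in 7.8.

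**The plan's own figure.** 24 / (1 − 0.20) = 30, so the stated enrolment reproduces. It refers to attrition during treatment and says nothing about loss afterwards.

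**Assumptions, because the documents give no values:**
- R = responders at visit 21: 9 to 15 of 30
- L = fraction of responders lost before 6 months: 10% to 30%
- r = fraction of responders who have relapsed by 6 months: 10% to 50%
- The HRSD is measured at follow-up.

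**Formulas for visit 21 responders still responding at 6 months, per 30 enrolled:**
- Carried forward: [R(1 − L)(1 − r) + R·L] / 30
- True rate if the lost relapse as often as those seen: R(1 − r) / 30
- Lost responders counted as not sustained: R(1 − L)(1 − r) / 30
- Overstatement by carrying forward: R·L·r / 30, or R·L / 30 if all the lost have relapsed

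**Middle case, R = 12, L = 0.20, r = 0.30:**
- Carried forward: (12 × 0.8 × 0.7 + 12 × 0.2) / 30 = (6.72 + 2.40) / 30 = 30.4%
- True, same relapse rate: 12 × 0.7 / 30 = 28.0%
- Lost counted as not sustained: 6.72 / 30 = 22.4%
- Overstatement: 30.4 − 28.0 = 2.4 points, or 30.4 − 22.4 = 8.0 points if all the lost have relapsed

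**Ends of the assumed range:**

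| | R | L | r | Same relapse rate | All lost relapsed |
|---|---|---|---|---|---|
| Low | 9 | 0.10 | 0.10 | 0.09 / 30 = 0.3 points | 0.9 / 30 = 3 points |
| High | 15 | 0.30 | 0.50 | 2.25 / 30 = 7.5 points | 4.5 / 30 = 15 points |

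**The same middle case among the 12 responders:** carried forward 9.12 / 12 = 76%; observed only 6.72 / 9.6 = 70%; lost counted as not sustained 6.72 / 12 = 56%. These are expected values, not possible counts.

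**The opposite term.** Suppose all 12 responders are among the 24 expected completers. Then 24 − 12 = 12 completers are non-responders. If the same fraction L of them is lost, and a fraction q of them would have responded by 6 months, carrying forward misses 12·L·q / 30. This cancels the responder term 12·L·r / 30 when q = r. The net direction therefore depends on quantities that the documents do not give.

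**The case against.** The strongest reply is that the plan lists no outcome that this rule would distort. A reader might infer that the HRSD response and remission rates themselves are inflated, or that they could be read from whichever visit looks best. The documents do not support that. The natural meaning of an outcome assessed after the course is the end of the course, in line with the visit 21 timing in 1.7 and the end-of-course timing in 7.3.3. On that reading, values carried into months 3 and 6 cannot change either rate. The missing visit label is an omission of detail.

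Other tempting inferences also fail:
- **A durability endpoint is biased.** None is listed. The problem is confined to whatever follow-up summaries are produced.
- **The plan calls its own population recurrent.** In 5.6 that word describes participants in the cited meta-analyses. Inclusion (3.1) requires a current episode.
- **Follow-up exists to detect relapse.** Section 4.8 gives no purpose, and 6.9 shows that safety is one use in the first 3 months.
- **The distortion is large.** Suppose 4 of 12 responders are lost and 4 of the 8 seen have relapsed. Carrying forward gives 8/12 (67%), and counting the lost as not sustained gives 4/12 (33%). Those counts are assumed and unfavourable, and the comparison sets opposite extremes against each other.
- **Carrying forward always flatters.** It also freezes non-responders. Those who leave during treatment carry a baseline or early score, which will often lower the response rate.

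Two points of the reply stand as limits. HRSD collection at follow-up cannot be confirmed without Appendix 2; if no symptom scale is collected then, the point about follow-up scores falls. The outcomes are also exploratory.

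The reply does not rescue the rule itself. A visit schedule would not narrow a rule that covers all missing data. The completer analysis does not clearly help, because if completion means reaching visit 21, completers' follow-up gaps are still filled.

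**Conclusion.** The point holds in a limited form. If symptom scales are measured at 3 and 6 months, section 7.8 makes the follow-up figures partly a product of imputation. For participants lost after improving, the bias is towards sustained benefit; over all participants its net direction is unknown.

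The documents do not determine the size. The ranges of 0.3 to 7.5 points (lost relapse at the same rate as those seen) and 3 to 15 points (all lost have relapsed) cover the responder term only and rest on the assumed R, L and r. Retention, acceptability at visit 21 and the enrolment of 30 are untouched. The change is still worth making, because a less biased report costs little and the results are to inform a larger trial.

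**What to change.** 1. **Section 7.8.** State that no value is carried forward into the 3- or 6-month assessments, whether from the treatment period or from month 3 to month 6.
2. **Follow-up reporting.** Report each of these timepoints on observed data with the number observed. Add a bound that counts end-of-course responders lost to follow-up as not sustained. The bound is needed because observed data alone are also biased if relapse drives loss.
3. **Section 1.6, as a clarification.** State that response and remission are assessed at the end of the course (visit 21), with 3 and 6 months reported separately.

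The cost is a few lines of SAP wording and one extra tabulation, with no new visits, data or participants. The downside is that follow-up results will rest on fewer people and may look less favourable. The change does not settle how dropouts during treatment are handled at visit 21; carrying forward would still apply to them under 7.8.

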1.4 Primary endpoint/outcome

The hypothesis is that there will be participant retention of 70% or greater.

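### Carrying the last score forward makes the ITT result for PHQ-9, HAMA and SDS a change to last contact, not a change over the 6-week course

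*Combined protocol and SAP*

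**What the plan says.** Section 7.8 consists of one sentence: "Any missing data will be imputed in a last observation carried forward model". It states no missingness assumption, alternative method or sensitivity analysis.

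Section 7.7 defines two analyses. In the first, "All participants will be included in the analysis in an intention to treat analysis". In the second, "participants who have completed the study will be included in a completer analysis".

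Section 7.1 plans an enrolment of 30 and gives the expected loss behind that number: "based on a 20% attrition rate to achieve a sample size of 24 participants who will complete the course of treatment". Section 1.4 sets the feasibility target: "The hypothesis is that there will be participant retention of 70% or greater".

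The affected outcomes are numbers 3, 4 and 6 in section 1.6. Number 3 reads "Improvement in self-reported depressive symptoms as measured by PHQ-9"; numbers 4 and 6 ask the same of HAMA and SDS. Section 7.3 describes analyses only for retention and acceptability, so these outcomes have no stated model, summary statistic or confidence interval.

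**The concern.** A participant who leaves in mid-course has no end-of-course score. Under 7.8 the last score obtained before leaving takes its place and is then treated as observed. The ITT mean therefore mixes change over the full course (completers) with change over a shorter, variable period (drop-outs). That is not the quantity a reader will take it to be.

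The direction of the error is not fixed. If drop-outs would have gone on improving, the mean change is too small. If they were getting worse when they left, a score from before the worsening is frozen and the mean change is too large. Carry-forward therefore cannot be defended as reliably conservative.

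Section 5.3 says the findings will be used in designing a powered sham-controlled trial. It does not say that these score changes will be used, but if they were, the distortion would go with them.

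This point covers in-course gaps on the symptom and disability scores only. Carry-forward to the 3- and 6-month visits and to the acceptability rating are separate matters.

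**Working it through.** **The plan's own figure.** 24 / (1 − 0.20) = 30, and 30 × 0.80 = 24. The figure in 7.1 reproduces, and it implies 6 drop-outs. At the 70% target, 30 × 0.30 = 9.

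**Inputs from the documents**
- Enrolment of 30 and 20% attrition: 7.1.
- Up to 30% attrition still compatible with success: 1.4.
- Course of 6 weeks, with 5 sessions a week for the first 3 weeks: 5.6. Visit 10 therefore falls at the end of week 2.

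**Assumptions, not in the documents**
- The target for outcomes 3, 4 and 6 is change to the end of the course.
- Drop-outs would have followed the completers' course.
- Drop-out times are spread evenly over 6 weeks.
- The assessment schedule is in Appendix 2, which is not visible, so three schedules are tried. The sparsest (baseline, visit 10, visit 21) borrows the visits that 4.1.3 names for the optional EEG only.
- Improvement is either linear, t/6, or front-loaded, (1 − e^(−t/2)) / (1 − e^(−3)).

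**Formula.** Relative understatement = d × (1 − f), where d is the drop-out share and f is the mean fraction of the final change already reached at the last score.

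**Values of f**
- Linear, continuous: 1/2 = 0.500.
- Linear, weekly: (0+1+2+3+4+5) / 36 = 0.417.
- Linear, sparse: 1/3 × 0 + 2/3 × 1/3 = 0.222.
- Front-loaded, continuous: (1 − 0.950/3) / 0.950 = 0.719.
- Front-loaded, weekly: mean of (0, 0.393, 0.632, 0.777, 0.865, 0.918) / 0.950 = 0.629.
- Front-loaded, sparse: 2/3 × 0.632 / 0.950 = 0.443.

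| Curve | Assessments | f | Understated, d = 20% | Understated, d = 30% |
|---|---|---|---|---|
| Linear | continuous | 0.500 | 10.0% | 15.0% |
| Linear | weekly | 0.417 | 11.7% | 17.5% |
| Linear | sparse | 0.222 | 15.6% | 23.3% |
| Front-loaded | continuous | 0.719 | 5.6% | 8.4% |
| Front-loaded | weekly | 0.629 | 7.4% | 11.1% |
| Front-loaded | sparse | 0.443 | 11.1% | 16.7% |

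**Bounds at d = 20%.** f = 0 gives 20%, f = 0.5 gives 10%, f = 1 gives 0%. If leavers' last scores showed more improvement than the final mean, f exceeds 1 and the sign reverses (f = 1.1 gives −2%).

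**Intervals, if reported.** An illustrative simulation used n = 30, a true PHQ-9 change of −8, SD 5, correlation 0.5, linear improvement, the sparse schedule and random drop-out.
- 20% attrition: bias 8 × 0.156 = 1.2 points; a nominal 95% interval covers about 77% to 80% of the time, depending on how drop-out is generated.
- 30% attrition: expected bias 8 × 0.233 = 1.9 points (1.7 to 1.9 in the simulations); coverage about 57% to 61%.
- Maximum likelihood and the completer analysis were both essentially unbiased here. The completer interval covered 95%.
- The mean half-width at 20% attrition was 2.02 under carry-forward against 2.10 for completers. With the bias removed, the carry-forward interval covers at least 95%.

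The coverage loss thus comes almost wholly from the interval being centred on a biased value.

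**The case against.** The strongest objection is that 7.7 already plans a completer analysis. Under the assumption behind every figure above, that drop-outs are otherwise like completers, that analysis is unbiased. This stands, and limits what the fix adds in that case. But the completer result can itself be biased if drop-out relates to outcome, and it leaves the ITT estimate as 7.8 defines it. The plan gives no rule for reading the two together.

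It is also fair to say that these outcomes are exploratory, in a single-arm pilot that 5.3 says is not powered for efficacy, and that retention needs no imputation. That stands and sets the weight of the point.

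Three stronger readings are tempting, and the documents do not support them.

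- **The bias is at least about 10%.** That needs f of 0.5 or less. The documents give neither a trajectory nor a visible schedule, and two of the six scenarios above fall below 10% at 20% attrition.
- **Scores are frozen at an early value.** They are frozen at the last value before drop-out. Without Appendix 2, whether that is early is unknown.
- **The confidence intervals are too narrow.** None is planned for these outcomes. In a separate grid of 16 assumed scenarios, the ratio of carry-forward to completer interval width ran from 0.81 to 1.06; it was below 1 in 15, but not in all. In the scenario with the marked coverage loss, width is not the main cause.

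**Conclusion.** The point holds in a limited form. By construction, the ITT analysis under 7.8 estimates change to last contact for about 6 of 30 participants at the plan's attrition, or 9 of 30 at the 70% target.

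If drop-outs would have followed the completers and leave evenly over the course, mean change is understated by roughly 6% to 16% at 20% attrition and 8% to 23% at 30%. Without the assumptions on timing and curve, the range at 20% attrition is 0% to 20%. If leavers were worsening, the error can run the other way. Any interval around the carry-forward mean would tend to under-cover, mainly because of that bias.

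This is an optional-level improvement to exploratory outcomes. It does not touch the primary retention result, and nobody should infer from it that the feasibility conclusion is at risk.

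**What to change.** In 7.8, replace carry-forward for the ITT analysis of PHQ-9, HAMA and SDS, and of any HRSD or YMRS score change, with a likelihood-based repeated-measures model:

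- use all observed in-course scores, with visit as a factor;
- use an unstructured covariance, and name in advance the simpler structure to be used if it does not converge at n = 30;
- report the change to end of course with a 95% CI.

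Keep the completer analysis in 7.7. Add one sensitivity analysis in which drop-outs keep their baseline score, for the case that they would not have improved. This is also single imputation, so read it as a bound and not as a second main estimate.

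The cost is SAP wording and standard software, with no new visits or data. The interval will be somewhat wider, and the model assumes data are missing at random given the observed scores. If Appendix 2 has no assessments between baseline and the end of the course, the gain over the completer analysis is small and the sensitivity analysis is the more useful part of the change.
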